7.6 Physical Examination

Physical examination data will be listed, but not summarized.

7.7 Performance Status

Performance status data (Karnofsky and Lansky) will be listed, but not summarized. Patients that are < 16 years when first assessed then are 16 or older at subsequent visits will have their scores reported appropriate to the age at the time of the assessment (Lansky for < 16 years, Karnofsky \geq 16 years).

7.8 Concomitant Medications

All concomitant medications will be coded using the WHO Drug, Version 2013Q1 or most recent version prior to database lock. The frequency of concomitant medications will be summarized using descriptive statistics by therapeutic class and preferred term. Patients are counted only once in each therapeutic class category, and only once in each preferred term category.

There will be two concomitant medication summaries provided: all medications taken while the patient takes Adagen[®] study drug and all medications taken while the patient takes EZN-2279.

7.9 Immunogenicity

The percentage of patients positive for each type of antibody will be summarized at baseline, each intermediate collection time-point, and endpoint.

Data regarding blood sample collections for antibody titers, and antibody levels for any positive tests, will be listed but not summarized.

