- Immunogenicity of EZN-2279 and Adagen® will be assessed through the end of the EZN-2279 maintenance period by the evaluation of binding antibodies, neutralizing antibodies and anti-PEG antibodies.

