### **9.3. Exclusion Criteria**

Patients meeting any of the following exclusion criteria will not be eligible for enrollment.

1. Autoimmunity requiring immunosuppressive treatment.
2. Patients with detectable neutralizing anti-Adagen® antibodies at screening evaluation.
3. Severe thrombocytopenia (platelet count  $< 50 \times 10^9/\text{L}$ ).
4. Current participation in other therapeutic protocols for ADA-deficient combined immunodeficiency.

5. Current or prior participation in another clinical study with an investigational agent and/or use of an investigational drug in the 30 days before study entry.
6. Known planned participation in a gene-therapy study for the planned duration of this study.
7. Any condition that, in the opinion of the PI, makes the patient unsuitable for the study.
8. Inability or unwillingness to administer Adagen® or EZN-2279 on a one time per week regimen.
9. Inability to comply with the study protocol.
10. Female patients who are pregnant or lactating.
11. Female patients who are breast-feeding.
12. Female patients of childbearing potential who are not using an FDA approved birth control method.

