#### 10.4.3.1. Immunogenicity

Venous blood samples for determination of anti-EZN-2279 and anti-Adagen® binding and neutralizing antibodies, and anti-PEG antibodies will be collected in 2mL ethylenediaminetetraacetic acid (EDTA) tubes at the timepoints listed in Appendix 2.

If the results of ADA activity indicate an unexpected reduction in activity from previous sampling timepoints, and if there is an adequate amount of sample remaining for analysis, assay for binding, neutralizing, and anti-PEG antibodies will be performed

Samples will be collected, processed and shipped to the central laboratory for analysis as described in the laboratory manual for the study.

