### 11.1. Screening

Patients who fulfill all of the inclusion criteria and none of the exclusion criteria may be entered into the study.

The following evaluations are to be performed within 28 days before start of the Adagen® Lead-in period unless otherwise indicated.

- Informed assent/consent
- Obtain patient history and baseline characteristics
  - Demographics
  - Disease background and history
  - Assessment of AEs/toxicities the patient has experienced while on Adagen® treatment
  - Assessment of infectious complications and hospitalizations within the past 12 months
  - Medical history
  - Medication history
- Physical examination
- Vital signs
- Height and weight for growth assessment
- Performance status score
- Urine or serum pregnancy test for females of childbearing potential must be performed within 7-days before starting Adagen® Lead-in.
- Safety Lab
  - Hematology
  - Serum chemistry
  - Urinalysis
- Immunogenicity - Adagen® antibody titers (i.e., neutralizing and binding antibodies) and anti-PEG antibodies

Patients passing screening assessment will enter the Adagen Lead-in phase of the study.

For patients currently maintained with Adagen® on a 1 time per week dosage regimen, the following additional laboratory assessments will be performed to determine whether an Adagen® dosage adjustment when entering the Adagen® Lead-in phase is required:

- Total erythrocyte dAXP from a trough blood sample
- Trough plasma ADA activity

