#### 11.3.22. Day 141 (Week T-21)

On Day 141 ( $\pm$  1 day) the patient will return to the study site and have the following procedures performed:

- Physical examination
- Height and weight for growth assessment
- Performance status
- Vital Signs
- Safety Lab
  - Hematology

- Chemistry
- Urinalysis
- Other labs – obtained 15 to 30 minutes prior to dosing
  - dAXP
  - Trough ADA activity
  - B-, T-, and NK-lymphocyte subset analysis
  - Quantitative immunoglobulins
  - EZN-2279 antibody titers (i.e., neutralizing and binding antibodies) and anti-PEG antibodies
- Adverse event assessment
- Assessment of infectious complications and hospitalizations
- Assessment of concomitant medications and procedures since last study visit
- Assessment of overall survival

The patient will receive his/her dose of EZN-2279 after all procedures and laboratory blood draws have been completed.

Following completion of assessments and dosing at Week T-21 the patient will enter the EZN-2279 maintenance period.

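### SAP 7.9 plans no count of patients who become antibody-positive on EZN-2279; per-visit percentages do not separate new or boosted antibodies from those present at T-1

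*SAP*

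**What the plan says.** The whole analysis is in SAP 7.9: "The percentage of patients positive for each type of antibody will be summarized at baseline, each intermediate collection time-point, and endpoint". Details of sample collection, and "antibody levels for any positive tests, will be listed but not summarized".

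Protocol 6.3.2 makes immunogenicity to both products a secondary safety endpoint, which "will be assessed through the end of the EZN-2279 maintenance period by the evaluation of binding antibodies, neutralizing antibodies and anti-PEG antibodies". Protocol 13.2.3 has each patient serve as his or her own control against baseline and gives antibody formation as an example.

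At entry, Protocol 9.3 excludes "Patients with detectable neutralizing anti-Adagen" antibodies at screening. It does not exclude binding or anti-PEG antibodies. Protocol 5.5 says that the EZN-2279 enzyme has the same bovine sequence as Adagen, and both products are PEGylated.

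Protocol 10.4.3.1 also adds unscheduled testing. "If the results of ADA activity indicate an unexpected reduction in activity from previous sampling timepoints", and enough sample remains, binding, neutralizing and anti-PEG assays are run.

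**The concern.** Possibly reduced immunogenicity is one stated reason for developing EZN-2279 (Protocol 5.4 and 6.1). The natural question is how many patients without an antibody at the switch acquire one on the new product, and how many with one show a rise. A percentage positive at each visit does not answer either. It counts a patient positive since the Adagen years in the same way as one who turned positive last week.

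The SAP makes this distinction for adverse events, where 7.3 counts those that are new or worsening on each therapy. It has no equivalent for antibodies.

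The word baseline in SAP 7.9 is also unclear. SAP 10.4 defines baseline as the last value before the first EZN-2279 dose but limits its use to efficacy endpoints, and 7.9 is in the safety section. For anti-PEG antibodies, baseline could mean screening, Adagen PK Day 1 or T-1.

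**Working it through.** The plan gives no figure for immunogenicity, so there is none to reproduce. The check has four parts.

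**1. What two percentages can identify.** Input: n = 6 evaluable patients (Protocol 13.1, SAP 3.2), all tested at both visits. If a patients are positive at T-1 and b at a later visit, the number newly positive at that visit lies between max(0, b − a) and min(b, n − a).

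- a = 3, b = 3: from max(0, 0) = 0 to min(3, 3) = 3.
- a = 2, b = 3: from max(0, 1) = 1 to min(3, 4) = 3.
- a = 0: both limits equal b, so nothing is mixed.

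Of the 7 × 7 = 49 possible pairs (a, b), 25 leave the number open: those with both a and b between 1 and 5. This counts possibilities and is not a probability.

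**2. An illustration over several visits (assumed pattern).** Two patients are positive throughout, a third is positive only at T-3 and a fourth only at T-10. The planned table reads 2/6, 3/6, 3/6, 2/6 at T-1, T-3, T-10 and T-21. Two of the four patients negative at T-1 became positive (2/4 = 50%), and 4/6 (67%) were ever positive. Neither figure is in the table. Even if a reader assumes that the two carriers stayed positive, there is 3 − 2 = 1 new positive at T-3 and one at T-10, and the table does not say whether this is one patient or two. A titre rise in either carrier would change no entry.

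**3. Where triggered assays can fall.** Appendix 2 schedules trough ADA at 13 visits from T-1 to T-21: T-1, 3, 5, 7, 8, 9, 10, 11, 13, 15, 17, 19 and 21. Immunogenicity is scheduled at four of them: T-1, T-3, T-10 and T-21. So 13 − 4 = 9 visits have an ADA result but no scheduled antibody draw, including T-15, T-17 and T-19, three of the four primary-endpoint visits. If one patient is tested at such a visit and is positive, the percentage is 1/1 = 100% of those tested or 1/6 = 16.7% of all. The SAP does not say which.

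**4. Which antibodies are named at which visit.**

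| Collection (Protocol section) | Antibodies named, besides anti-PEG |
|---|---|
| Screening (11.1) | Adagen |
| Adagen PK Day 1 (11.2.3.1) | Adagen |
| T-1 (11.3.1) | EZN-2279 and Adagen |
| T-3, T-10, T-21 (11.3.3, 11.3.11, 11.3.22) | EZN-2279 |
| Maintenance (11.4), end of study (11.5) | EZN-2279 |

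Screening asks for "Adagen® antibody titers (i.e., neutralizing and binding antibodies) and anti-PEG antibodies", T-21 for "EZN-2279 antibody titers (i.e., neutralizing and binding antibodies) and anti-PEG antibodies". Anti-Adagen antibodies are thus named at none of the five collection types after T-1. Yet 6.3.2 carries them through maintenance, and 10.4.3.1 calls for both anti-EZN-2279 and anti-Adagen samples at the Appendix 2 time-points. Those include T-3, T-10, T-21 and maintenance, and the appendix does not split its column by product.

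**Precision after the fix.** With 0 new positives among m patients negative at T-1, the exact two-sided 95% upper limit is 1 − 0.025^(1/m). The documents do not give m, so a range is shown:

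| m | 6 | 5 | 4 | 3 | 2 |
|---|---|---|---|---|---|
| Upper limit | 45.9% | 52.2% | 60.2% | 70.8% | 84.2% |

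The chance of seeing at least one new positive is 1 − (1 − p)^m. For an assumed true rate p of 10% it is 46.9% with m = 6 and 27.1% with m = 3. For 20% it is 73.8% and 48.8%.

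**The case against.** The strongest reply is that nothing is lost. SAP 7 lists all safety data, 7.9 lists the level of every positive test, and positivity at baseline is itself tabulated. With about six patients, new, boosted and ever-positive status can be read by hand. Protocol 13.2.3.5 also relates immunogenicity to PK and toxicity. This stands: the gap is a definition and a table. The mock displays and patient profiles (SAP Appendices B and C) are separate documents, so a baseline-by-later display there cannot be ruled out.

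Carry-over is also limited for neutralizing antibodies, because detectable ones at screening exclude the patient. That stands too, apart from any arising between screening and T-1. The concern is mainly about binding and anti-PEG antibodies.

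Three stronger readings are tempting, and the documents do not support them.

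- *Triggered positives enter no percentage.* SAP 7.9 covers each collection time-point, and SAP 10.4 includes unscheduled visits in by-visit summaries. The difficulty is the irregular denominator.
- *A transient or triggered response would be missed.* It would be in the listings. It would not be in a planned incidence.
- *Adagen antibodies are not collected after T-1, so the endpoint should be narrowed.* Protocol 10.4.3.1 with Appendix 2 can be read as requiring both assays at every immunogenicity draw. The visit lists read otherwise. That is a contradiction, and it does not show which text is intended.

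On the unclear baseline, SAP 10.6 takes EZN-2279 safety changes from the end of lead-in. This makes T-1 the likely reading but does not state it for antibodies.

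**Conclusion.** The point holds as a reporting gap of low severity. SAP 7.9 does not deliver the within-patient comparison that Protocol 13.2.3 intends for antibody formation. At n = 6, the planned percentages leave the number of new positives open in 25 of 49 possible pairs of counts, and boosted titres never show. How much this matters depends on how many patients are positive at T-1, which the documents do not give; at zero, nothing is mixed. The bounds assume six patients, all tested at both visits.

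Separately, Protocol 6.3.2, 10.4.3.1 with Appendix 2, and the Section 11 visit lists disagree on whether anti-Adagen antibodies are assayed after T-1. The primary endpoint and the sample size are not affected by either issue.

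**What to change.** In SAP 7.9:

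- Name the pre-dose T-1 sample as the immunogenicity baseline. It is the first visit whose list names EZN-2279 antibodies, and SAP 10.2 already assigns T-1 assessments to Adagen.
- Add one table per antibody type of treatment-emergent incidence on EZN-2279. *Induced* means negative at T-1 and positive at any later sample, triggered ones included, over those negative at T-1. *Boosted* means positive at T-1 with a titre rise above a fold threshold set before results are seen.
- Give counts with exact 95% intervals, and keep the per-visit percentages as supportive, with the denominator stated for visits that have only triggered assays.

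In the protocol, reconcile 6.3.2, 10.4.3.1, Appendix 2 and the Section 11 visit lists on anti-Adagen antibodies after T-1. Either the later visits name that assay or the endpoint states where it stops; the sponsor must say which was meant.

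The SAP change costs some wording, one extra table from data already planned and a pre-set threshold. The intervals will be wide, so the table supports description only. Reconciliation costs either added assays at visits where an immunogenicity sample is already drawn or a narrower endpoint.

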8. PHARMACOKINETIC ANALYSIS

A full description of planned analyses are detailed in the PK analysis plan, Appendix A

9. STATISTICAL SOFTWARE

All data listings, summaries, and statistical analyses will be generated using SAS[®] Version 9.1 or higher.²

Phoenix[®] WinNonlin[®] Version 6.1 or higher³ will be used for the calculation of pharmacokinetic parameters and the statistical analysis of steady-state data.

² SAS Institute Inc. 2004. SAS/STAT[®] 9.1 *User's Guide*. Cary, NC: SAS Institute Inc.

³ Pharsight[®], a Certara[™] company

10. RULES AND DEFINITIONS

10.1 Timing of Analyses

The initial three patients will be enrolled and complete through full EZN-2279 pharmacokinetic sampling (Week T-9). An independent data and safety monitoring committee (DSMC) will review safety, PK (ADA activity), and erythrocyte dAXP data. If no concerns are noted, enrollment will continue for the remaining three patients. A similar DSMC review will occur for EZN-2279 dosing for the following:

- All six patients who complete through (Week T-9).
- All six patients who complete through (Week T-21).
- All six patients who complete one year (i.e. two maintenance cycles).

Listings will be produced for the BLA when three subjects have complete data through final analysis (one year/two maintenance cycles). The BLA will include all patients enrolled at that time.

10.2 Association with Study Drug

Assessments collected at EZN-2279 Day 1 (Week T-1) are associated with Adagen[®] treatment because EZN-2279 is not administered until all procedures are complete. All endpoints are measured in comparison to screening or the Adagen[®] Lead -in phase (baseline), as appropriate, within each patient.

10.3 Assignment of Study Days

For the purposes of data listings and summaries, “Study Day” will be calculated relative to the first dose of study medication (i.e., date of interest – date of first dose of Adagen[®]). One day will be added if this difference is ≥ 0 , so that the first dose of study medication is considered “Study Day- 1.” The day prior to the first dose of study medication is considered “Study Day -1”. For analysis purposes, there will be no “Study Day- 0”.

10.4 Screening, Baseline and Study Weeks

No windowing schemes will be applied to the data. For by-visit summaries, if there are multiple assessments at a post baseline visit then the last non-missing assessment at that visit will be used for the summary. This includes assessments at the scheduled and unscheduled visits. For Patients who withdraw from the study, data at the early termination visit will be excluded from the by-visit summaries but will be included in the endpoint summaries.

Screening is defined as the last measurement for a variable before the initial dose of Adagen[®] study drug. With the exception of adverse events and medications, assessments collected at the screening visit are associated with the screening period because Adagen[®]

is not administered until all procedures are complete. Adverse events and medications starting on the day of the first dose of Adagen[®] are associated with Adagen[®] treatment.

Baseline is defined as the last measurement for a variable before the initial dose of EZN-2279 study drug, and is only used as the starting point for efficacy endpoints. With the exception of adverse events and concomitant medications, assessments collected at EZN-2279 Day-1 (Week T-1) are associated with Adagen[®] treatment because EZN-2279 is not administered until all procedures are complete. Adverse events and concomitant medications starting on the day of the first dose of EZN-2279 are associated with EZN-2279 treatment.

With regard to screening and baseline determination, assessments falling exactly on the date of the first dose of each study medication will be considered pre-dosing for that medication with the exception of adverse events and concomitant medications, which will be associated with the respective study drug.

Missing data will not be imputed.

10.5 Efficacy Data Handling

Change from baseline to Week X in efficacy endpoints will be calculated from the end of the Adagen[®] Lead-in period as:

- (Endpoint Value at Week X) – (Endpoint Value at Baseline), where baseline is defined as in Section 11.4.

10.6 Safety Data Handling

For the purposes of AE reporting, three time periods will be defined based upon the onset date of the AE:

- “Pre-treatment AEs” are AEs with onset dates < date of the first dose of Adagen[®] study medication.
- “Treatment-emergent AEs” are AEs with onset dates \geq date of the first dose of study medication and within 30 days following the date of the last dose of study medication.
- “Post-treatment AEs” are AEs with onset dates > 30 days after the date of the last dose of study medication, within study STP-2279-002.

“Pre-treatment” and “Post-treatment” AEs are considered non-treatment-emergent AEs. For AEs with partially missing onset dates, an onset date is imputed as detailed in Section 12 (Programming Specifications). If an AE has a completely missing onset date, it is

counted as a “treatment-emergent” event, unless the stop date is on or before the date of the first dose of study medication.

If relationship to study drug is missing, for analysis purposes it will be assumed to be related to study drug. For AEs which occur more than once within a time period (see above), the AE which is most related to study drug in that time period will be used in the summary of AEs by categories of relationship to study drug. Similarly, the AE with the maximum intensity in that time period will be used in the summary of AEs by categories of severity.

For each study drug (EZN-2279 or Adagen[®]) medications will be assigned to a time period as follows:

- Medications taken any time < date of the first dose of Adagen[®] during the Lead-in phase will be considered prior medications.
- Medications can be concomitant with either Adagen[®], EZN-2279, or both. Medications taken any time \geq date of the first dose of respective study medication and within 30 days following the date of the last dose of respective study medication will be considered concomitant medications for that study drug.
- Medications taken > 30 days after the date of the last dose of respective study medication will be considered “post treatment” medications for that study drug.

Note that medications can be counted in more than one category (i.e., prior/concomitant) and can have different assignments for different study drugs. Imputation rules for partially missing start/stop dates are described in Section 12 (Programming Specifications).

Change from baseline to Week X in safety endpoints will be calculated as:

- Adagen[®] Drug Group: (Endpoint Value at Week X) – (Endpoint Value at Screening), where screening is defined as in Section 11.4.
- EZN-2279 Drug Group: (Endpoint Value at Week X) – (Endpoint Value at End of Adagen[®] Lead-in phase).

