### 12.3. Reporting Adverse Events

All new events, as well as those that worsen in intensity or frequency relative to baseline, which occur must be captured. The Investigator or his/her staff should elicit information regarding the occurrence of adverse events through information volunteered by the patient, open-ended questioning of the patient, physical examination results and review of laboratory results.

Information to be recorded for each AE includes:

- A medical diagnosis of the event (if a medical diagnosis cannot be determined, a description of each sign or symptom characterizing the event should be recorded)
- The date and time of onset of the event
- The date and time of resolution of the event
- Assessments of severity, causal relationship, and seriousness of the adverse event (see definitions in Section 12.2.1 through 12.2.4)
- Action(s) taken (if any) for management of the adverse event, including but not limited to change in the study drug administration (e.g., temporary interruption in dosing, dose reduction); drug treatment; non-drug treatment; diagnostic procedures performed
- Outcome of the adverse event: e.g., patient recovered without sequelae; patient recovered with sequelae; event ongoing; patient died

If a medical condition is known to have caused the injury or accident (e.g., a fall secondary to dizziness), the medical condition (dizziness) and the medical condition resultant to the fall (hip fracture) should be reported as two separate AEs. The act of falling (i.e., fall) should be recorded as part of the event term in the CRF.

All adverse events will be followed until resolution, stabilization, or for 30 days after last dose of study drug, whichever occurs first.

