### 13.2.3.5. Safety Data Analysis

Adverse Events and Serious Adverse Events – AEs will be categorized using Medical Dictionary for Regulatory Activities (MedDRA) Version 10.0 or later. The intensity of toxicities will be graded by the Investigator as mild, moderate, or severe as described in Section 12.2.5. Serious Adverse Events (SAEs) will be a subset of the overall AE analysis and may be analyzed in a similar manner.

The calculation of AE incidence will be based on the number of patients per AE category. For each patient who has multiple AEs classified to the same category, that patient will be tabulated under the maximum toxicity intensity for that AE category. The incidence of AEs will be tabulated by MedDRA system organ class and preferred term, as well as by treatment group.

An AE onset between the date of the first dose of study drug and 30 days after the last dose of study drug is considered as a treatment-emergent AE.

- Laboratory Safety Data – Hematology, chemistry, and urinalysis data will be summarized by timepoint of collection and by treatment group. In addition, out-of-normal range values will be listed.
- Other Safety Data – the results of antibodies against EZN-2279, antibodies against Adagen®, and antibodies against PEG will be summarized. The relationships between immunogenicity, PK, and the clinical toxicities will be examined as appropriate.

Concomitant medications and findings in physical examinations will be described textually as recorded in the CRF.

Descriptive statistics of vital signs measurements as well as changes from baseline will be tabulated.

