7.3 Adverse Events and Other Complications

All adverse events will be coded using the Medical Dictionary for Regulatory Activities (MedDRA) Version 16.0 or the most recent version prior to database lock. Summaries will be presented for all treatment-emergent adverse events (overall and by severity), adverse events determined by the investigator to be treatment-related (overall and by severity), serious adverse events (SAEs), adverse events causing discontinuation from study, adverse events causing discontinuation from study drug, and non-serious adverse events. In addition to being summarized as adverse events, infectious complications and hospitalizations are considered efficacy measures as are summarized in Section 6.3.

The frequency of adverse events will be summarized using descriptive statistics by system organ class (SOC), preferred term and study drug group. Patients are counted only once in each SOC category, and only once in each preferred term category.

Treatment-related adverse event summaries will include adverse events with missing relationship to study drug. For the summaries by severity, patients are counted at the greatest severity. Adverse events missing the flag indicating serious will be excluded from the summary of serious adverse events but included in the summary of non-serious adverse events.

There will be two treatment emergent adverse event summaries provided: all treatment emergent adverse events while the patient takes Adagen[®] study drug and all treatment emergent adverse events while the patient takes EZN-2279, where treatment emergent are new or worsening adverse events that occur while on the respective therapies.

Listings for all adverse events, deaths, serious adverse events, adverse events leading to discontinuation, MedDRA dictionary terms for adverse event descriptions, and adverse event preferred terms by patient number will be presented.

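### SAP 7.3 and SAP 10.6 define treatment-emergent adverse events differently, so an event that begins on lead-in Adagen and worsens on EZN-2279 can be lost from the EZN-2279 table.

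*SAP*

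**What the plan says.** **Per-drug tables.** SAP 7.3 plans two treatment-emergent summaries, one for Adagen and one for EZN-2279, "where treatment emergent are new or worsening adverse events that occur while on the respective therapies".

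**Period rule.** SAP 10.6 states that "three time periods will be defined based upon the onset date of the AE": pre-treatment, treatment-emergent and post-treatment. An event is treatment-emergent if its onset falls on or after the first dose of study medication and "within 30 days following the date of the last dose of study medication". Protocol 13.2.3.5 also uses onset only: "An AE onset between the date of the first dose of study drug and 30 days after the last dose of study drug". Neither text mentions worsening or splits the window by drug.

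**Link to a drug.** SAP 10.4 works from the start date and addresses only first-dose days, for example: "Adverse events and concomitant medications starting on the day of the first dose of EZN-2279 are associated with EZN-2279 treatment".

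**Severity.** SAP 7.3: "For the summaries by severity, patients are counted at the greatest severity". SAP 10.6, on events that occur more than once in a period: "Similarly, the AE with the maximum intensity in that time period will be used in the summary of AEs by categories of severity". The same section selects the strongest relationship to study drug in the same way.

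**Capture.** Protocol 12.3: "All new events, as well as those that worsen in intensity or frequency relative to baseline, which occur must be captured". The fields listed in Protocol 10.4.4 and 12.3 include onset, resolution and severity. No date of worsening is listed.

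**Consequence for the tables.** SAP 11 restricts the summary tables to treatment-emergent events, so the definition decides what appears in them.

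**The concern.** Every patient moves from Adagen to EZN-2279, so some events may be ongoing at the switch. SAP 7.3 would put such an event in the EZN-2279 table if it then worsened. SAP 10.6 gives the programmer only an onset date to work with, and that date lies in the lead-in. The two rules can therefore produce different tables from the same data.

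The contrast with medications in SAP 10.6 is telling. Medications are assigned by reference to the respective study drug and may count under one drug or both. Adverse events have no equivalent rule.

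The by-drug tables are the main summary of the safety of a product which, according to Protocol 5.3.2, had not been studied clinically before. Post-switch worsening is one of the things they should show.

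**Working it through.** The plan gives no figure on this point, so there is none to reproduce. The check applies each rule to one hypothetical event and then shows what one event is worth at this sample size.

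**Inputs.** Lead-in of 3 weeks, the minimum in Protocol 7.1.1. Adagen doses are then assumed on study days 1, 8 and 15, with the first EZN-2279 dose on day 22. Week T-21 is EZN-2279 Day 141, which is study day 22 + 140 = 162. The event is assumed to start on day 10 as mild and to become severe on day 40. Six evaluable patients (SAP 3.2).

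**One event under three readings**

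| Reading | Adagen table | EZN-2279 table |
|---|---|---|
| A. Onset rule, one record updated to its worst grade | severe | none |
| B. SAP 7.3 rule, new or worsening | mild | severe |
| C. Onset rule, worsening entered as a new record | mild | severe |

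In A, day 10 lies between day 1 and day 162 + 30 = 192, so the event is treatment-emergent. Day 10 is before day 22, so by start date it belongs to Adagen. In C, the second record starts on day 40, after day 22, and so belongs to EZN-2279. Only A departs from what SAP 7.3 promises.

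**Event present before lead-in.** If the recorded onset is before day 1 and the event worsens on treatment, SAP 10.6 classes it as pre-treatment, hence not treatment-emergent, and SAP 11 keeps it out of every summary table. SAP 7.3 would count it.

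**Separate records.** Suppose a patient has the same event twice, mild on Adagen and severe on EZN-2279. Both fall in the one treatment-emergent period of SAP 10.6, so the maximum is severe, and nothing confines it to the EZN-2279 table. With the grades reversed, a severe grade reached on Adagen could be carried to EZN-2279. Record splitting alone does not cure this.

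**Partial dates.** Under SAP 11, an event with day and month missing, in the year of the first Adagen dose, is given that dose date. An event that began on EZN-2279 in the same year would then carry a lead-in onset.

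**The 30-day window at the switch.** If it is read per drug, the Adagen window ends on day 15 + 30 = 45, while the EZN-2279 window opens on day 22. An event starting on day 30 lies in both. The overlap runs from day 22 to day 45, or 45 − 22 + 1 = 24 days. The SAP does not say whether the window is meant this way.

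**Scale** (Clopper-Pearson 95% limits, n = 6)
- 0/6 = 0%; upper limit 1 − 0.025^(1/6) = 45.9%.
- 1/6 = 16.7%; limits 0.4% to 64.1%.

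One reclassified event can move an incidence from one of these lines to the other.

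**The case against.** The strongest reply is that SAP 7.3 is the only text that defines the two per-drug tables, and it includes worsening. SAP 10.6 does not allocate events to a drug; its three periods cover the whole study. SAP 10.4 speaks only to first-dose days. A programmer who follows SAP 7.3 gets reading B. Protocol 12.3 requires worsening to be captured, which is compatible with a new record. The CRF instructions are not among the documents and the mock displays are in a separate companion file, so record-splitting practice is unseen rather than shown to be absent. All events are listed, serious events and deaths have their own listings, the DSMC reviews safety repeatedly, and no decision rule depends on these counts.

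Much of this stands, and it rules out stronger readings that a reader might infer:

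- *Every such event is charged to Adagen at its worst grade.* No text says so. It needs both the onset rule and a single record updated to its maximum.
- *The error always favours EZN-2279.* Readings B and C produce no error. The severity rule can act in either direction, and SAP 10.4 assigns to EZN-2279 any event starting on its first-dose day, even before the injection.
- *One event shifts the between-drug difference by 2 × 16.7 = 33.3 points.* The SAP plans separate descriptive summaries and no such difference. Exposure is also unequal: at least 3 weeks of lead-in against 21 weeks plus maintenance.

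What the reply does not remove is the contradiction. SAP 10.6 is a data-handling rule that defines the same term as SAP 7.3 without the worsening criterion. Listings let a reader find an individual event, but they do not settle which table it belongs in.

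**Conclusion.** The point holds as a conflict between two definitions in one SAP, joined by a severity and relationship rule whose period spans both drugs. Under the onset-only rule, an event that starts on lead-in Adagen and worsens on EZN-2279 can be absent from the EZN-2279 table; its appearance under Adagen at its worst grade further assumes one record. The effect of the cross-drug maximum does not depend on that assumption.

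The number of affected events cannot be obtained from the documents and may be zero. The 0/6 to 1/6 scale assumes six patients and no other event of that category in the same patient on that drug. The as-treated denominator may exceed six, since SAP 3.2 allows more to be enrolled. The primary endpoint is not touched. The correction should be made before the safety tables are programmed.

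**What to change.** 1. In SAP 10.6, replace the onset-only rule with the SAP 7.3 definition applied per drug: onset or worsening on or after the first dose of the respective drug. Align SAP 10.4, and note the difference from Protocol 13.2.3.5 in SAP 7.1 or amend that section.
2. Take maximum severity and strongest relationship within each drug's period, not across both.
3. In Protocol 12.3 and the CRF instructions, require worsening after the first EZN-2279 dose to be recorded with its own start date and grade.
4. State how the 30-day window applies at the switch, so that it is clear whether an event in the overlap counts under one drug or both.

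The cost is a few SAP sentences, one protocol sentence and a CRF instruction. The downside is that a worsened event can appear once in each drug's table, so EZN-2279 counts may be slightly higher. That is what SAP 7.3 already implies, and a table footnote can say so.
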